In general, low dose, physiologic dosed steroid use has consistently shown to reduce vasopressor requirements, but mortality benefit remains controversial despite multiple randomized, controlled trials (RCTs). Recent meta-analyses have concluded that uncorrected data do not demonstrate mortality benefit¹. Of the main RCTs conducted in the past 20 years, there are two main differences between those that find mortality benefit with steroid use (APROCCHSS and Ger-Inf-05) and those that do not (CORTICUS, HYPRESS, and now ADRENAL). The first difference is the use of fludrocortisone in combination with the standard dose of hydrocortisone 200 mg intravenously (IV) daily. The second difference is the focus on patients with septic shock who did not improve after initial resuscitation and were requiring higher baseline doses of vasopressors. The trials finding mortality benefit enrolled sicker patients at baseline than the trials that did not find mortality benefit, which was identified through a variety of severity scores (APACHE, SAPSII, and SOFA) and baseline mean vasopressor doses^{2,3}. For example, baseline SOFA scores were on average 12 in the treatment arm of the APROCCHSS trial versus 10.6 in the CORTICUS trial^{3,4}. In addition, mean norepinephrine doses at randomization in the ADRENAL trial were 30 mcg/min, whereas the mean norepinephrine dose at randomization in the APROCCHSS trial was 1 mcg/kg/min (70 mcg/min in a 70 kg patient)^{3,5}.

The theory for use of fludrocortisone centers around data that suggests 40-65% of critically ill patients have high plasma renin activity and low plasma aldosterone concentrations². Moreover, experimental sepsis studies in murine models have suggested that a marked NF- κ B mediated down-regulation of mineralocorticoid receptors occurs during the

shock process. Administration of aldosterone in mice resulted in improved response to phenylephrine⁶. Based on the RCTs performed in human subjects, however, it is controversial whether addition of fludrocortisone provides any true benefit in refractory septic shock patients. Moreover, to date there has not been a trial, whether retrospective or prospective, that has directly compared the use of hydrocortisone alone versus the combination of hydrocortisone and fludrocortisone. Because of this lack of data, we will be investigating the use of hydrocortisone alone versus the combination in critically ill septic shock patients admitted to the medical intensive care unit. Currently, both are considered standard of care both within and outside of the University of Tennessee Medical Center Knoxville.

Objective: To determine if the use of hydrocortisone plus fludrocortisone is associated with a faster resolution of shock (defined as 24 hours vasopressor free) when compared to the use of hydrocortisone alone in medical, critically ill septic shock patients

Study Design and Methods:

This study is a single-center, prospective, open-label, randomized trial which will evaluate adult patients admitted with septic shock to the medical critical care unit (MCC).

Inclusion Criteria:

- Age \geq 18
- Critically ill medicine patients requiring addition of stress dose steroid therapy (hydrocortisone) in addition to pressors for septic shock management during their ICU stay
- Fludrocortisone administered within 24 hours after initiation of hydrocortisone if in combination therapy group

Exclusion Criteria:

- Use of fludrocortisone and/or hydrocortisone for any reason other than septic shock management during ICU stay
- Fludrocortisone/hydrocortisone initiated by any service other than critical care medicine
- Prior use of fludrocortisone/hydrocortisone at time of admission (home or outside facility)
- Patients not appropriate for study inclusion as determined by provider discretion
- Patients receiving steroid therapy not in accordance with assigned group per location (MCC1 or MCC2)
- Patients re-admitted to the MCC during the same admission and restarted on vasopressor therapy will be noted during data collection and only the initial admission will be included for analysis
- Any patient receiving greater than one dose of hydrocortisone 100 mg
- Physical or medical contraindication to receiving PO or PER FT (per feeding tube) fludrocortisone.

Protocol:

All patients admitted to the medical critical care unit side 1 (MCC1) or side 2 (MCC2) will be provided a “Notice of Research.” At any time, refusal or withdrawal from the study can be requested by the patient, patient advocate, or provider.

Patients that meet inclusion criteria for the study will receive either hydrocortisone 50 mg IV Q6h alone or a combination of hydrocortisone 50 mg IV Q6h plus fludrocortisone 50 mcg PO/PER FT daily. Fludrocortisone must be initiated and administered within 24 hours after the first administered dose of hydrocortisone. Because fludrocortisone is only available as a 100 mcg tablet, the nurse at the bedside will split the tablet into two as to provide a 50 mcg dose. This is standard of practice currently when fludrocortisone is utilized in our institution.

Steroid therapy assignments will be randomized based on patient location. For three consecutive months starting in October 2018, all patients in MCC1 will receive hydrocortisone alone and all patients admitted to MCC2 will receive hydrocortisone plus fludrocortisone. Then, in the following three consecutive months, this will be flipped and MCC1 will receive hydrocortisone plus fludrocortisone while MCC2 will receive hydrocortisone alone. This change in group assignments will occur to account for the difference in number of beds between MCC1 and MCC2, and to minimize the potential differences in patient acuity by location.

Initiation of hydrocortisone for inclusion in the study will be determined solely by provider discretion as the standard of care for septic shock patients. Once hydrocortisone is initiated, fludrocortisone will be initiated within 24 hours for patients on the qualifying side of the unit, unless any of the previously stated exclusion criteria are present. Because these interventions are currently utilized and considered standard of care in the MCC, data collection will be performed retrospectively by generating a list of patients in the MCC receiving hydrocortisone therapy.

While each included patient’s data will be recorded retrospectively after randomization, we do believe that it is necessary to perform this study in a prospective manner rather than fully retrospective. It is not feasible to perform this study retrospectively as we would not be able to ensure adequate and equal numbers in each group within the medical critical care unit, especially considering how medical critical care patients are placed in other intensive care units within our institution based on bed availability. Unequal groups would unduly bias the results and make the analysis less meaningful in terms of contributing to the current body of evidence.

Any medication events, including adverse drug reactions or medication errors, will be routinely reported throughout the study to the UTMC Safety Intelligence system. Routine reports of events related to the study will be reviewed weekly by our medication safety office if necessary. Data will be collected continuously throughout the study duration and investigators will review the data for any concerning safety or efficacy differences between the treatment groups. Upon regular screening for adverse drug events, if any are detected, they will be not only be reported to the Safety Intelligence system but will also be reported for review by the IRB.

Per the FDA guidance for clinical investigators regarding the need for an investigational new drug (IND) application in human research studies, investigations are exempt if the drug is lawfully marketed in the U.S., the investigation is not intended to support a new indication or change the labeling of the drug, the investigation will not support a change in advertising for the drug, and the route of administration, dose, or any other factor of the investigation will not increase the risk associated with the drug⁷. Our study, since we are not changing standard of care and are using accepted, studied doses of hydrocortisone and fludrocortisone, meet these criteria for exemption from IND application.

Outcomes:

- Primary Endpoint:
 - Time to resolution of shock (defined as 24 hours vasopressor free)
- Secondary Endpoints:
 - ICU Length of Stay (LOS)
 - Hospital LOS
 - All-cause mortality at ICU discharge
 - All-cause mortality at hospital discharge
 - All-cause mortality at 28 days of admission
 - All-cause mortality at 90 days of admission
 - Withdrawal of treatment therapy during ICU stay
 - Reinitiation of vasopressor therapy (after vasopressor free for 24 hours)
 - Reinitiation of hydrocortisone and/or fludrocortisone
 - Mechanical ventilator free days during ICU admission
 - Duration of steroid therapy
- Safety Endpoints
 - Documentation of two consecutive point of care blood glucose checks >180 mg/dl after initiation of hydrocortisone and/or hydrocortisone/fludrocortisone
 - Gastrointestinal bleed during study period (as documented by provider)
 - Severity of bleed as determined by GUSTO criteria
 - Severe: deadly bleeding; intracerebral bleeding or substantial hemodynamic compromise
 - Moderate: bleeding requiring transfusion
 - Mild: other bleeding not requiring transfusion or causing hemodynamic compromise
 - New initiation of renal replacement therapy during study period
 - Electrolyte abnormalities
 - Sodium level greater than 150 mEq/L during study period
 - Potassium level greater than 5.5 mEq/L during study period

Other Data Collected:

- Demographics: Age, sex, weight, height, BMI, ethnicity (race)
- Septic Shock Bundle initiated
- WBC at time of steroid initiation and at discontinuation

- Initial lactic acid level on admission
- Lactic acid level at initiation of vasopressors
- Vasopressor initiated (norepinephrine, epinephrine, phenylephrine, vasopressin, dopamine, dobutamine)
- Vasopressor dose when steroid therapy was initiated (mcg/min and mcg/kg/min)
- Max vasopressor dose during study period
- SOFA Score
- APACHE Score
- Charlson Comorbidity Index
- Site of infection (lung, intraabdominal, urogenital, skin, CNS, endocarditis, bacteremia, unknown, etc.)
- Non-contaminant, positive culture during study period with clinical correlation to septic shock event
 - Site of culture
 - Gram Positive
 - Gram Negative
 - Viral
 - Fungal
 - Organism
- Comorbidities:
 - Documented heart failure
 - Documented chronic kidney disease stage III-IV not requiring renal replacement therapy at baseline
- Documentation of concurrent cardiogenic shock during study period
- Serum creatinine at initiation of steroid therapy
- Serum creatinine at discontinuation of steroid therapy
- Renal replacement therapy at the initiation of steroid therapy
- Mechanical ventilation at initiation of steroid therapy
- Other systemic steroid use (methylprednisolone, dexamethasone, prednisone) prior to pressor initiation
- Systemic steroid use prior to admission (home medication)
- Continuation of baseline/prior steroid in combination with hydrocortisone/fludrocortisone
- Inhaled corticosteroid use
- Intubation with etomidate
- Amount of diuretics received during study period
- Acute respiratory distress syndrome documented during study period
- Administration of neuromuscular blocker during study period

Statistical Analysis:

Statistical Power

In order to achieve adequate statistical power for the proposed prospective trial, an a priori sample size calculation was completed based on an evidence-based measure of effect size from the APROCCHSS and CORTICUS trials^{3,4}. The evidence-based difference between the treatment groups was 24 hours (Group 1 $M = 96$, $SD = 36$; Group 2 $M = 72$, $SD = 36$), leading to a Cohen's d effect size of 0.67. With a two-tailed hypothesis, an effect size of $d = 0.67$, an alpha value of 0.05, and equal allocation to treatment groups (1:1), 39 participants would be needed for each treatment group. This means the total sample size will be $n = 78$ in order to achieve adequate statistical power for the trial.

Statistical methods

Frequency and percentage statistics will be used to analyze categorical demographic, predictor, confounding, and outcome variables of interest for the sample. Descriptive statistics will be used to describe the sample characteristics associated with continuous variables. The assumption of normality of continuous distributions will be assessed using skewness and kurtosis statistics. If either statistic is above an absolute value of 2.0, then the distribution will be assumed to be non-normal. Homogeneity of variance between independent groups will be tested using Levene's Test for Equality of Variances. When both statistical assumptions are met, independent samples t-tests will be used to compare the treatment groups on continuous outcomes. Means and standard deviations will be reported and interpreted for these analyses. Mann-Whitney U tests will be used for comparisons when statistical assumptions are violated. Medians and interquartile ranges will be presented and analyzed for non-parametric comparisons. Chi-square tests will be used to test for significant associations between the treatment groups and categorical outcomes. Relative risk with 95% confidence intervals will be reported for significant categorical associations. Multiple regression analysis will be performed with time to resolution of shock as the outcome. Linearity, normality, homoscedasticity, multicollinearity, and autocorrelation assumptions for the regression analysis will be performed. Unstandardized beta coefficients, standard errors of the coefficients, and standardized beta coefficients will be reported and interpreted, along with the change in shared variance (R^2) and respective F-tests. All analyses will be conducted using SPSS Version 22 (Armonk, NY: IBM Corporation) and statistical significance will be assumed at an alpha value of 0.05.

A priori subanalysis will be performed on the following subset of patients: documented history of heart failure and documented chronic kidney disease stage III and IV requiring renal replacement therapy at baseline.

Critical Analysis/Limitations:

Limitations of this study will include the open-label design without blinding and placebo controls. Also, as data collection will be retrospective in nature, we will be relying on nursing documentation for timing of vasopressor initiation and discontinuation for our primary outcome. This could introduce documentation bias, but it is important to point out that our critical care nursing staff document pressor requirements hourly. Also, to note, previous trials have utilized fludrocortisone 50 mcg doses. Currently, the only commercially available fludrocortisone product in the United States is a 100 mcg tablet. In order to comply with the

previously studied dose and the current guideline recommended therapy, we will be utilizing fludrocortisone 50 mcg in our study. This will be achieved by splitting the available 100 mcg tablet in half. Education will be provided to all providers, pharmacists, and nursing involved in the project about the correct dose for fludrocortisone and the appropriate way to order the dose.

Protected Health Information:

Patients and their specific health information will be de-identified to protect privacy. Any information collected that contains PHI will be stored in a secure, locked area on password-protected electronic files that are only accessible to study investigators. Any information containing PHI will be properly disposed of at the end of the study period.

Study Budget: Cost of printing of notification of research

Timeline:

Estimated October 2018 through July 2019

References:

1. Long B and Koyfman A. Controversies in corticosteroid use for sepsis. *J Emerg Med.* 2017; 53 (5): 653-661.

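### The primary comparison is unadjusted, and the planned regression has no named covariates or role, so the collected baseline vasopressor dose is not committed to the treatment estimate

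*Combined protocol and SAP*

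**What the plan says.** All references are to the combined protocol and SAP.

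- **Background and Rationale.** Severity is one of two features said to separate positive from negative steroid trials, described as the "focus on patients with septic shock who did not improve after initial resuscitation and were requiring higher baseline doses of vasopressors". The section adds: "The trials finding mortality benefit enrolled sicker patients at baseline than the trials that did not find mortality benefit". The examples are SOFA 12 versus 10.6, and norepinephrine of about 70 versus 30 mcg/min.
- **Inclusion Criteria.** The entry condition is "Critically ill medicine patients requiring addition of stress dose steroid therapy (hydrocortisone) in addition to pressors for septic shock management during their ICU stay". No threshold is set for vasopressor dose, SOFA, APACHE or lactate.
- **Protocol.** "Initiation of hydrocortisone for inclusion in the study will be determined solely by provider discretion". The regimen depends on unit side (MCC1 or MCC2). The sides exchange regimens after three months, partly because bed numbers differ and partly to limit acuity differences by location.
- **Other Data Collected.** The list includes "Vasopressor dose when steroid therapy was initiated (mcg/min and mcg/kg/min"), as well as SOFA, APACHE and lactate. SOFA and APACHE have no stated time point.
- **Statistical methods.** When assumptions are met, "independent samples t-tests will be used to compare the treatment groups on continuous outcomes"; otherwise a Mann-Whitney test is used. A multiple regression with time to resolution of shock as outcome is also planned, but its covariates, any selection rule and its standing relative to the t-test are not given. The a priori subsets concern "documented history of heart failure and documented chronic kidney disease stage III and IV" and do not include severity.

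**The concern.** A patient on a higher vasopressor dose when steroids start can be expected to take longer to come off vasopressors. Baseline dose is therefore a natural prognostic variable for this endpoint, and the protocol itself treats severity as important. The plan nevertheless leaves open whether dose enters the treatment comparison at all.

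Two things are at stake. The first is precision: with 39 patients per arm, an unadjusted test gives up information already on the collection list. The second is bias. Allocation is by location and calendar period, and whoever starts hydrocortisone knows which regimen follows, so severity need not be balanced as it would be in expectation under concealed individual randomization.

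Leaving the covariates to be chosen later is weak protection. The trial is open-label, and the Protocol section has the investigators reviewing accumulating safety and efficacy differences.

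**Working it through.** **Inputs from Statistical Power:** means 96 and 72 h, SD 36 h in each group, two-sided alpha 0.05, 1:1 allocation, 39 per group. No power figure is stated.

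**Assumed, not in the documents:** a within-arm correlation r of 0.3 to 0.5 between baseline vasopressor dose and time to resolution; the size of any severity imbalance; a recorded time for every patient.

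**1. The plan's own figure.** d = 24/36 = 0.667. At 80% power a two-sample t-test needs 37 per arm. Dividing by the Mann-Whitney efficiency 3/pi = 0.955 gives 37/0.955 = 38.7, so 39. The stated 39 is reproduced at about 80% power. With 39 per arm, the t-test has power 0.83.

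**2. Precision gained by adjustment.** Residual SD = 36 x sqrt(1 - r^2). SE of the difference = residual SD x sqrt(2/39), where sqrt(2/39) = 0.226. Equivalent unadjusted total = 78/(1 - r^2).

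| | Residual SD (h) | SE (h) | SE reduction | Power at 39 per arm | Equivalent unadjusted total |
|---|---|---|---|---|---|
| Unadjusted | 36.0 | 8.15 | - | 0.83 | 78 |
| r = 0.3 | 34.3 | 7.78 | 5% | 0.86 | 86 |
| r = 0.5 | 31.2 | 7.06 | 13% | 0.92 | 104 |

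**3. Bias from a systematic imbalance.** Bias = imbalance (SD) x r x 36 h.

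- 0.25 SD: 0.25 x 0.3 x 36 = 2.7 h, to 0.25 x 0.5 x 36 = 4.5 h. This is 11 to 19% of the planned 24 h, or 0.33 to 0.55 of the unadjusted SE.
- 0.2 SD with r = 0.3 (2.2 h): power is 0.75 if the imbalance runs against the combination arm; with no true effect, the false-positive rate is 0.058.
- 0.3 SD with r = 0.5 (5.4 h): power 0.62; false-positive rate 0.10.

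**4. What the swap does and does not balance.** Suppose MCC1 supplies 60% of patients in each period and MCC2 40% (assumed; the documents say only that bed numbers differ).

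| | Hydrocortisone alone | Combination |
|---|---|---|
| First period | 60 (MCC1) | 40 (MCC2) |
| Second period | 40 (MCC2) | 60 (MCC1) |

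Each arm draws 60% from MCC1, so a stable side difference cancels. But 60% of the hydrocortisone-alone arm comes from the first period, against 40% of the combination arm. Any change in acuity over time therefore remains as an arm difference.

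**5. Selective entry.** The provider decides on hydrocortisone knowing the regimen attached to that side and month. Combination patients must also receive fludrocortisone within 24 hours, and patients treated off-assignment are excluded. A patient who dies or deteriorates before the first fludrocortisone dose can thus be lost from the combination arm alone. Exchanging the sides does not correct this.

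**The case against.** **The regression is already planned.** It is, and the descriptive part of Statistical methods mentions confounding variables. A reader might infer that baseline dose is never used; the documents do not support that, because it could enter this model. What remains is that nothing commits it to the model or makes the model the basis for inference.

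**The swap is a stated safeguard against acuity differences by location.** This stands for differences that are stable over time. It does not reach period effects, patient-level imbalance or selective entry.

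**Broad eligibility does not confound the arms.** A reader might infer that failing to enrich for severity repeats the confounding seen between earlier trials. It does not: those were separate trials in different populations, whereas here both regimens run concurrently in one unit under the same entry trigger. Lack of enrichment affects whom the result describes and may dilute an effect limited to sicker patients.

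**Refractory shock is not the stated target.** The Background remarks that "it is controversial whether addition of fludrocortisone provides any true benefit in refractory septic shock patients", but the Objective names medical, critically ill septic shock patients without that restriction. Needing stress-dose steroid on top of pressors already selects for some severity. A reader might infer that a null result would say nothing about refractory shock; the documents do not support so strong a claim. The Background contrast also concerns mortality, not shock resolution.

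**Chance imbalance must not be counted twice.** The unadjusted SE of 8.15 h already contains it. A one-SE chance imbalance (0.226 SD) moves the difference by 2.4 to 4.1 h at r = 0.3 to 0.5, which is the component whose removal yields the 5 to 13% gain. The 2.7 to 4.5 h figure is a separate cost only if the imbalance is systematic. The documents make such an imbalance plausible but do not quantify it.

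**Linear regression loses the Mann-Whitney fallback.** This is fair, and the adjusted analysis needs its own provision for skewed times.

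**Conclusion.** The concern holds as a gap in the analysis plan: the group comparison is unadjusted, the regression has neither named covariates nor a role, and a relevant baseline variable is already being collected. The design makes residual severity imbalance plausible despite the swap, but the documents do not show that it will occur.

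The likely gain is moderate: a 5 to 13% smaller standard error, and protection against a bias of a few hours if a 0.25 SD systematic imbalance arises. Both sizes rest on the assumed correlation, a linear relation on the hour scale and, for the bias, the assumed imbalance. Below r = 0.3 the gain is smaller; at r = 0.2 power would be 0.84. Adjustment reduces selective-entry bias but cannot remove it. The change is worth making because it is cheap and must be fixed before the data are examined.

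**What to change.** In Statistical methods:

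1. Make the planned regression on time to resolution of shock the primary treatment estimate.
2. Prespecify its terms: arm; vasopressor dose at the first hydrocortisone dose (log scale, with the conversion between agents fixed in advance); unit side; period. Add SOFA or APACHE if recorded at steroid start, and state that time point in Other Data Collected.
3. State the provision for skewed times: a log-transformed or rank-based outcome in the same model.
4. Keep the t-test or Mann-Whitney test as supportive, and tabulate baseline severity by arm.
5. A dose-by-treatment term is optional. If included, label it exploratory, since it will be imprecise at n = 78.

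**Cost.** SAP wording, an agreed vasopressor conversion and possibly a time point for the severity scores; the vasopressor dose itself is already collected. Side and period terms cost little precision. With the 60:40 split above, the variance factor for the arm effect is (1/4) x (2/0.3 + 2/0.2) = 4.17 instead of 4, so the SE rises by about 2% (sqrt(4.17/4) = 1.02). With only four side-by-period cells, anything peculiar to one cell still cannot be separated from the arm effect; the report should say so.

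### Receipt of fludrocortisone within 24 h is an entry condition in one arm only, patients not treated as assigned are excluded, and no as-allocated analysis is planned

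*Combined protocol and SAP*

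**What the plan says.** Study Design and Methods describes the trial thus: "This study is a single-center, prospective, open-label, randomized trial". Under Protocol, "Steroid therapy assignments will be randomized based on patient location": each side of the medical critical care unit has one regimen for three months, then the sides swap. A patient's group is thus fixed by unit side and date.

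Two eligibility rules then depend on treatment actually given. The Inclusion Criteria list "Fludrocortisone administered within 24 hours after initiation of hydrocortisone if in combination therapy group". The Exclusion Criteria list "Patients receiving steroid therapy not in accordance with assigned group per location (MCC1 or MCC2"). The first rule applies to the combination group only, the second to both groups.

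The cohort is found afterwards: "data collection will be performed retrospectively by generating a list of patients in the MCC receiving hydrocortisone therapy". Statistical methods compares the treatment groups by t-test or Mann-Whitney test, chi-square test and multiple regression. No section defines an analysis population, an as-allocated or intention-to-treat comparison, or a sensitivity analysis that restores excluded patients. Critical Analysis/Limitations does not mention the issue.

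**The concern.** The 24 h criterion can be judged only after up to a day of follow-up, and only one arm has to pass it. A combination-side patient who dies, has care withdrawn or stops steroids before the first fludrocortisone dose leaves the data set. A like patient on the hydrocortisone-alone side stays in. The arms can then differ with no treatment effect at all.

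The routes pull in different directions. Losing early deaths flatters the combination on the mortality endpoints. Losing patients who recover and stop steroids early removes short times to resolution, which counts against the combination on the primary endpoint. Other reasons for non-receipt could act either way. Because this is the only analysis set, a reader would have no second comparison in which to see the effect.

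**Working it through.** **Inputs from the documents (Statistical Power).** Means 96 h and 72 h, SD 36 h, two-sided alpha 0.05, 39 per group. No power target is named.

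**The plan's own figure.** With d = 24/36 and an assumed 80% power, the t-test needs 36.3, so 37 per group. Dividing by the Mann-Whitney efficiency of 0.955 gives 39. Power at 39 per group is 83.7% (normal approximation) or 82.8% (t-test). The sample-size arithmetic is not the problem.

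**(a) Mortality.** Assumed: 40% mortality, no true effect, e% dying in the first 24 h evenly over time, and first fludrocortisone doses uniform over 0 to T h. Per 100 combination patients, the number lost by dying before their first dose is x = e × T/48. Observed mortality is (40 − x)/(100 − x), against 40/100 in the other arm.
- T = 24: e = 5 gives 37.5/97.5, RR 0.96; e = 10 gives 35/95, RR 0.92; e = 15 gives 32.5/92.5, RR 0.88.
- T = 6: RR 0.99, 0.98 and 0.97.
- Two-sided type I error at 39 per group (pooled z-test, simulated): about 5%, 6% and 7% for T = 24, and about 5% throughout for T = 6.

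This route is not carried over to the primary endpoint, because the plan gives no time-to-resolution value for patients who die.

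**(b) Time to resolution, early recoverers only.** Assumed: Y ~ Normal(96, 36), counted from the first hydrocortisone dose. Vasopressors stop at U = Y, or at U = Y − 24 if the clock includes the 24 vasopressor-free hours. A combination patient is dropped if U falls before the first fludrocortisone dose F. The shift is E[Y | U ≥ F] − E[Y].

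Worked case, everyone with U < 24 lost:
- U = Y: share dropped Φ(−72/36) = 2.3%; shift 36 × 0.0540/0.9772 = 2.0 h.
- U = Y − 24: share dropped Φ(−48/36) = 9.1%; shift 36 × 0.1640/0.9088 = 6.5 h.

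Shift in hours, against the combination (other cells by numerical integration):

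| Clock and distribution | F uniform 0–6 h | F uniform 0–24 h | All with U < 24 lost |
|---|---|---|---|
| U = Y, plain normal | 0.5 | 1.0 | 2.0 |
| U = Y, truncated at 0 | 0.1 | 0.6 | 1.6 |
| U = Y − 24, plain normal | 2.4 | 3.9 | 6.5 |
| U = Y − 24, truncated at 24 | 0.4 | 1.9 | 4.5 |

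The plain normal includes impossible times, so the truncated rows are more realistic. For a given dosing time, every cell is an upper bound for this route. The Protocol section ties fludrocortisone to the start of hydrocortisone, not to continued vasopressor need, so a patient already weaned may still receive it on time and stay in.

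The Statistical Power section states: "The evidence-based difference between the treatment groups was 24 hours". On the plain normal, 1.0 to 2.0 h is 4% to 8% of that difference, and 3.9 to 6.5 h is 16% to 27%.

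**(c) Power of an as-allocated analysis.** If a share r of the combination arm gets no fludrocortisone and no benefit, power = Φ((24/36)(1 − r)√(39/2) − 1.96). For r = 0, 5%, 10% and 20% this is 83.7%, 79.9%, 75.5% and 65.4%. The values of r are assumed.

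**The case against.** *The 24 h wording is a treatment instruction.* The Protocol section gives that instruction separately: "Fludrocortisone must be initiated and administered within 24 hours after the first administered dose of hydrocortisone". The same condition also stands among the inclusion criteria, and the exclusion for non-assigned therapy reinforces it.

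*The question is about use.* The objective reads "To determine if the use of hydrocortisone plus fludrocortisone is associated with a faster resolution of shock". That supports a treatment-received analysis as an addition. It does not support a receipt rule applied to one arm as the only analysis.

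*Non-receipt may be rare.* Limitations plans education of providers, pharmacists and nurses on dose and ordering, which should reduce it, and 24 h is an outer limit rather than the expected dosing time. This stands, and it is why the 6 h figures matter.

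*An as-allocated analysis would not be clean either.* This stands too. Unblinded providers start hydrocortisone knowing the side's assignment, and the two unit sides are swapped once. A reader might infer that the fix restores an individually randomized comparison. It removes one layer of selection only.

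*Stronger readings.* A reader might infer that the plan is biased toward the combination; the early-recovery route runs the other way on the primary endpoint. A reader might also construct large false-positive rates. If a share f is dropped and differs by s hours from the overall mean, the spurious difference is f × s/(1 − f). With f = 20% and s = 36 h this is 0.2 × 36/0.8 = 9 h, with about 17% false positives. The documents give neither f nor s, so the point does not rest on such figures.

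**Conclusion.** The concern holds in a limited form. Followed exactly, the plan compares every endpoint only in groups selected on treatment received. One selection rule applies to the combination arm alone, and nothing in the plan shows the groups as allocated. That absence is the reason to change it, not a demonstrated large bias.

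The true size and net direction cannot be determined from the documents. All early-death rates, dosing times and non-receipt shares used here are assumed, as is counting from the first hydrocortisone dose. On those assumptions the mortality distortion is modest, and close to nil with prompt dosing. The primary-endpoint figures are ceilings for one route, and that route works against the combination.

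**What to change.** - **Primary analysis set:** all otherwise eligible patients in the unit started on hydrocortisone for septic shock, analysed by the group assigned to their unit side at the first hydrocortisone dose, whatever was given afterwards. Use only exclusions that can be assessed by that dose, and apply them alike in both arms.
- **Per-protocol sensitivity analysis, so labelled:** keep the 24 h receipt rule and the assigned-therapy exclusion here, with a 24 h landmark in both arms.
- **Reporting:** give exclusions and withdrawals by arm, reason and time.
- **Limitations:** state that selection at hydrocortisone initiation by unblinded providers remains, and that a single swap of two unit sides is not individual randomization.

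**Cost.** Revised wording, plus chart abstraction for patients now excluded. The planned list of hydrocortisone recipients, with unit side and date, gives each patient's assigned group; the number of extra patients is not stated. Power at 39 per group falls from about 84% to about 80%, 75% or 65% at the assumed 5%, 10% or 20% non-receipt. Fludrocortisone given on the hydrocortisone-alone side would dilute the contrast further. The plan should restate its expected power on this basis. More patients need not be required, since no power target or enrolment rate is given.
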